**Sample of healthy volunteers for fMRI pilot:**

Participants who previously enrolled in IRB #4815 or 6786 or 7653 or 7172 as a healthy volunteer may be re-contacted to ask about their interest in current study participation, if they have already given written consent to be re-contacted about future studies.

### Inclusion/Exclusion Criteria

Name the subject group/sub sample

Neuroimaging participants

Create or insert table to describe the inclusion criteria and methods to ascertain them

Neuroimaging participants with NSSI: Inclusion Criteria	Method of Ascertainment
1. Age 18-60	Remote interview
2. Frequent current NSSI (including cutting in which the skin is broken; self-hitting in which there is bruising; or burning in which there is evidence of a burn. Will not enroll if skin-picking or scratching is the only form of self-injury): has engaged in $\geq 2$ episodes of NSSI in the two months prior to enrollment	Remote Self Injurious Thoughts and Behaviors (SITBI) scale and remote clinical interview
3. Capacity to provide informed consent	Remote clinical interview
4. If carries a diagnosis of bipolar I or II disorder, taking or willing to begin a therapeutic dose of a mood stabilizer*	Remote SCID, remote clinical interview, therapeutic blood levels if applicable
5. Normal hearing	Remote interview
6. Physical capacity (e.g., manual dexterity) to set-up and self-administer tDCS	Remote interview

\* If not currently taking a mood stabilizer, the participant will have the option of beginning mood stabilizer with a psychiatrist on our team. We would perform any necessary blood testing to screen for appropriateness of mood stabilizer treatment and to monitor blood levels. We would provide psychiatrist visits and any necessary blood testing, but would not cover the costs of mood stabilizer medication. If participants continue to meet all other eligibility criteria upon achieving a therapeutic dose of mood stabilizer, we would proceed with research participation. If they do not, we would forego research procedures and offer 3 months of open treatment.

Create or insert table to describe the exclusion criteria and methods to ascertain them

Neuroimaging participants with NSSI: Exclusion Criteria	Method of Ascertainment
1. Unstable medical conditions based on medical history or medical assessment	Medical history (by a physician), medical assessment as conducted in IRB #4815
2. Current psychotic disorder, mania, hypomania, intellectual disability	Remote psychiatric interview and SCID
3. Dermatologic condition resulting in non-intact skin on the scalp	Medical history
4. Significant suicidal ideation with a plan and intent that cannot be managed safely as an outpatient	Remote C-SSRS, remote clinical interview
5. Pregnancy, currently lactating, or planning to conceive during the course of study participation*	Urine HCG on days of MRI scans prior to scanning
6. A neurological disease or prior head trauma with evidence of cognitive impairment. Subjects who endorse a history of prior head trauma and score $\geq 1.5$ standard deviations below the mean on the Trailmaking A&B will be excluded from study participation.	Remote clinical interview and medical history, Trailmaking A & B as

	needed.
7. Current alcohol or substance use disorder that is severe according to DSM-5 criteria	Remote SCID and clinical interview
Individuals who initiated or increased the dose of concurrent psychiatric medications (including	Remote clinical interview and medical history
8. antidepressants, anxiolytics, antipsychotic medications, and mood stabilizers) within two weeks prior to enrollment	Remote clinical interview
9. Individuals who initiated psychotherapy within two weeks prior to enrollment	Remote clinical interview and medical history
10. Current seizure disorder	Remote clinical interview and medical history
11. Use of anticonvulsant medications that target the GABA system (e.g., gabapentin)	Remote clinical interview and medical history
Individuals currently using benzodiazepines who are unable or unwilling to refrain from the use of	Remote clinical interview and medical history
12. benzodiazepine medications for at least 72 hours before the first tDCS session and throughout the duration of the 2-week tDCS intervention**	Remote clinical interview and medical history
Metal implants or paramagnetic objects contained within the body (including heart pacemaker, shrapnel, or surgical prostheses) which may present a risk to the subject or interfere with the MRI scan, according to the guidelines set forth in the following reference book commonly used by neuroradiologists: "Guide to MR procedures and metallic objects," F.G. Shellock, Lippincott Williams and Wilkins NY 2001. Additionally, transdermal patches will be removed during the MR study at the discretion of the investigator.	Remote clinical interview, MRI safety screening forms
14. Claustrophobia significant enough to interfere with MRI scanning	Remote clinical interview and medical history
15. Weight that exceeds 325 lbs or inability to fit into MRI	Weight and

scanner

maximal body  
circumference  
(if necessary)  
as self-  
reported; visit  
to the MRI  
suite if  
necessary\*\*\*

**16**

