**. Suicide attempt within the past 3 months**

**Remote  
clinical  
interview  
and medical  
history**

**17 Serious self-harm resulting in hospitalization within  
. the past 3 months.**

**Remote  
clinical  
interview  
and medical  
history**

\*For females of childbearing age: Urine pregnancy test is performed during the screening procedure and urine pregnancy test is repeated on MRI scanning day. Since this test cannot detect the very early stage of pregnancy (the 10-day period between fertilization and implantation), an effective birth control method or sexual abstinence is required during the 15 days before the scans.

\*\*Individuals currently using benzodiazepines will be converted to an equivalent dose of a short-acting benzodiazepine, which they may continue to use until 72 hours before the first tDCS session.

\*\*\*In cases where there is a question about whether a participant's dimensions are compatible with the MRI scanner, a subject's circumference may be measured to determine if the subject's circumference is less than the MRI scanner limit, 200 cm. The subject also may be brought to the MRI center so that the MRI technologist can assess whether or not the subject will fit safely inside the MRI scanner. Metal screening and urine pregnancy testing will be done before this brief visit. Subjects who cannot safely enter the scanner will not be eligible to participate in the scanning portion of the study but may elect to remain in the study as a non-imaging subject.

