### Sample of patients with NSSI:

Following preliminary determination of eligibility, informed consent procedures will be conducted by the physicians listed in the following section. Initial screening will be completed as detailed in IRB #4815. For all remote procedures, the consenter will connect with the subject over the phone or a videoconference and will go through all relevant documents, including the HIPAA form and consent form, with the participant.

Participants will provide an electronic signature through RedCap's e-signature option. Consent for remote clinical or research procedures will be documented, and the consent discussion process will include discussion of the technology HIPAA-compliant platforms to be used and any concerns the patient may have, such as access to a private space in which to take calls, or accessibility—access at home to adequate devices, cell signal, or Wi-Fi. There will be a consent procedure note that includes that there was a discussion of risk related to COVID-19 during travel. Consent discussions will include informing participants of the option to reschedule if travel does not seem safe and/or the study team may offer alternative transportation, such as Uber or Lyft.

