### **Sample of patients with NSSI:**

All of the study procedures are listed below. Participants who enroll in the arm of the study without neuroimaging will follow all procedures described below with the exception of the neuroimaging-related procedures (MRI). Participants will follow all procedures described below remotely, with the exception of the neuroimaging-related procedures (MRI). For females of childbearing age, a urine HCG test will be sent by mail with instructions detailing how to use the test. Participants will be asked to photograph the results of the test and upload them through RedCap or attach.nyspi.org. For both arms of the study, participants will have the option of receiving tDCS in-person or remotely.

Subjects who frequently engage in NSSI will be recruited as described above and will co-enroll in the brief medical assessment arm of IRB Protocol #4815. Following informed consent for participation, screening evaluation will be performed at study entrance through IRB protocol #4815 and will include a complete medical history and remote clinical examination to exclude significant physical illness.

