## **Criteria for Early Discontinuation**

### Criteria for Early Discontinuation

A CGI-Improvement score at any time point of 6 or 7 ("much worse" or "very much worse") will trigger clinical evaluation by the study investigators, Drs. [name] or [name], for possible study discontinuation. We will assess suicidal ideation and behavior weekly from the time of consent through the completion of tDCS procedures. If individuals endorse suicidal ideation that includes a plan and intent, or have made an actual suicide attempt, research procedures will be discontinued, and open clinical treatment will be initiated immediately at an appropriate level of care.

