### Criteria for Early Discontinuation

A CGI-Improvement score at any time point of 6 or 7 ("much worse" or "very much worse") will trigger clinical evaluation by the study investigators, Drs. [name] or [name], for possible study discontinuation. We will assess suicidal ideation and behavior weekly from the time of consent through the completion of tDCS procedures. If individuals endorse suicidal ideation that includes a plan and intent, or have made an actual suicide attempt, research procedures will be discontinued, and open clinical treatment will be initiated immediately at an appropriate level of care.

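### Exclusion 4 can admit patients with suicidal plan and intent whom the stopping rule must then remove in the same state; the entry wording should match the stopping rule (minor)

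*Combined protocol and SAP*

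**What the plan says.** **Entry.** Exclusion 4 for neuroimaging participants (Inclusion/Exclusion Criteria) reads "Significant suicidal ideation with a plan and intent that cannot be managed safely as an outpatient". The remote sample (Inclusion/Exclusion Criteria #4) has the same wording, as does the non-imaging sample (Inclusion/Exclusion Criteria #2), which is not recruiting. The method of ascertainment is the C-SSRS with a clinical interview, both done remotely in the two active samples.

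**Stopping.** Criteria for Early Discontinuation, printed once on its own and again under Assessment Instruments, says: "If individuals endorse suicidal ideation that includes a plan and intent, or have made an actual suicide attempt, research procedures will be discontinued". It adds that "open clinical treatment will be initiated immediately at an appropriate level of care". On timing it says: "We will assess suicidal ideation and behavior weekly from the time of consent through the completion of tDCS procedures".

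**Other suicide-related entry criteria.** All three patient tables also exclude "Suicide attempt within the past 3 months" and recent self-harm that led to hospitalisation. Neither criterion concerns current ideation.

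**The concern.** The entry rule has two conditions: plan and intent must be present, and outpatient management must be unsafe. The stopping rule has one: plan and intent. It has no outpatient qualifier and does not require that anything has changed since entry. A patient who meets the first entry condition but not the second therefore passes exclusion 4, and the stopping rule then requires removal in the same state.

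At stake is avoidable burden on a high-risk group: taking someone into a study that the study's own safety rule says they cannot continue. In the worst ordering of events, that burden could include procedures done before the first stimulation session.

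**Working it through.** No arithmetic decides this point; it is a comparison of two rules.

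**Step 1. Compare the rules over every combination of plan and intent and outpatient manageability.**

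| Patient's state | Exclusion 4 | Stopping rule (ideation trigger) | Consistent? |
|---|---|---|---|
| No plan and intent | Not excluded | Continues | Yes |
| Plan and intent, not manageable as an outpatient | Excluded | Discontinued | Yes |
| Plan and intent, manageable as an outpatient | Not excluded | Discontinued | **No** |

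One cell is inconsistent. If exclusion 4 ended at plan and intent, the third row would read excluded and discontinued, and the inconsistency would be gone.

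**Step 2. Look for another criterion that covers the third row.** There is none. The attempt and hospitalised self-harm exclusions look back over three months at behaviour. The stopping rule's other trigger, an actual attempt, does have an unqualified counterpart at entry in 3 of 3 patient tables; plan and intent has one in 0 of 3. The parallel is not exact, because one is a three-month history and the other is an event found during monitoring.

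**Step 3. Count the wording.** The outpatient qualifier is in 3 of 3 patient exclusion tables, 2 of them active. It is in neither printing of the stopping rule, which is one rule printed twice. These counts describe the text, not patients.

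**Step 4. Find where the two rules meet.**

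- Consent Procedures puts a preliminary check first: "Following preliminary determination of eligibility, informed consent procedures will be conducted".
- Study Procedures puts the full evaluation after consent: "Following informed consent for participation, screening evaluation will be performed at study entrance through IRB protocol #4815". The stopping rule is already in force by then.
- The eligibility tables name the C-SSRS for exclusion 4, but the Timing of Psychological Assessments table first marks it at Baseline, prior to session 1. That table also omits the weekly C-SSRS during tDCS that the text of Assessment Instruments requires, so it is not a full schedule. The missing Enrollment mark does not show that no screening C-SSRS is done.
- The tDCS section gives no timing for random assignment.
- The screening protocols (#4815 and #6879R) were not available.

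**Step 5. Range of burden per affected patient.**

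- *Lower end:* plan and intent is acted on at the first check after consent. The burden is little more than screening.
- *Upper end:* plan and intent is first acted on at the Baseline C-SSRS. By then the patient may have started the pre-treatment EMA week and, in the imaging sample, had a baseline scan. A benzodiazepine user may have been switched to a short-acting agent and begun to abstain from "benzodiazepine medications for at least 72 hours before the first tDCS session". If randomisation also came first, the stop would be a post-randomisation withdrawal unrelated to tDCS.

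The upper end requires that neither the eligibility C-SSRS nor the weekly checks from consent led to action.

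**The case against.** **The stopping rule already catches these patients.** Ideation is to be assessed weekly from consent, and discontinuation is mandatory. A patient with plan and intent should be stopped at the first check, with treatment started at once. In practice this is a screen failure with care attached. This stands, and it is why the point is minor.

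**The stopping rule may be meant for change during the study.** Assessment Instruments describes the weekly C-SSRS as watching for emergent ideation, the EMA section speaks of treatment-emergent ideation, and the rule sits beside a CGI trigger for worsening. The rule itself contains no such condition, however, and it runs from consent, before any stimulation. It is also firmer than its neighbour: the CGI trigger leads only to an evaluation that may end in discontinuation, whereas plan and intent ends research procedures outright.

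**The outpatient clause may only describe plan and intent, not limit it.** The two rules would then coincide. But the clause would be doing no work, and deleting it would cost nothing. The stopping rule also leaves the level of care open, so it does not presume that such patients always need inpatient care.

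**The stopping rule could be amended instead.** Adding the outpatient qualifier there, or limiting the rule to new or worsened ideation, would also restore consistency. That is true, and the choice is a judgement. Aligning entry to the stopping rule is the more protective option: it leaves a safety rule intact and loses no patient whom the trial could keep in that state.

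**Conclusion.** The mismatch is real and minor. As written, exclusion 4 admits patients with current plan and intent if they are judged manageable as outpatients, and the stopping rule must remove them unchanged. Confidence in that reading is high; confidence about how many are affected, and how soon they would be stopped, is low. The reading assumes that the word significant in exclusion 4 adds no separate threshold once plan and intent are present.

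A reader might infer more than the documents support:

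- *That the two rules cannot both be obeyed.* They can, in sequence. The fault is that following both enrols a patient only to remove that patient.
- *That patients are left at risk.* The mismatch fails safe, because research stops and treatment starts.
- *That affected patients will go through EMA, scanning or a benzodiazepine washout before being stopped, or be lost after randomisation.* This happens only if the state is first acted on at the Baseline C-SSRS and, for the last, only if randomisation comes earlier. The schedule does not settle either.
- *That results are biased.* No effect on a defined endpoint is shown.
- *That many patients are involved.* The documents give no rate, and none can be calculated from them.

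**What to change.** In the neuroimaging and remote tables, end exclusion 4 after the word intent, so that any current ideation with plan and intent is excluded at entry. Do the same in the non-imaging table if that sample reopens. State that the criterion is applied on the eligibility C-SSRS already named there, before benzodiazepine conversion, randomisation or session 1. Leave both printings of the stopping rule unchanged.

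The cost is one clause deleted in two active tables and one sentence on sequence. No new instrument is needed. The downside is a few more screen failures, including some patients whose ideation might have eased before session 1. Planned non-completers should not be treated as room for these: 50 − 22 = 28 (imaging) and 50 − 24 = 26 (remote) are already attributed to expected ineligibility, withdrawal and missed appointments.

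Two additions are optional. A C-SSRS mark in the Enrollment column of the timing table would make the check visible. Open treatment could be offered to people excluded before consent, but the stopping rule does not require it, so it would be a new commitment of psychiatrist time.

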**. Suicide attempt within the past 3 months**

**Remote  
clinical  
interview  
and medical  
history**

**17 Serious self-harm resulting in hospitalization within  
. the past 3 months.**

**Remote  
clinical  
interview  
and medical  
history**

\*For females of childbearing age: Urine pregnancy test is performed during the screening procedure and urine pregnancy test is repeated on MRI scanning day. Since this test cannot detect the very early stage of pregnancy (the 10-day period between fertilization and implantation), an effective birth control method or sexual abstinence is required during the 15 days before the scans.

\*\*Individuals currently using benzodiazepines will be converted to an equivalent dose of a short-acting benzodiazepine, which they may continue to use until 72 hours before the first tDCS session.

\*\*\*In cases where there is a question about whether a participant's dimensions are compatible with the MRI scanner, a subject's circumference may be measured to determine if the subject's circumference is less than the MRI scanner limit, 200 cm. The subject also may be brought to the MRI center so that the MRI technologist can assess whether or not the subject will fit safely inside the MRI scanner. Metal screening and urine pregnancy testing will be done before this brief visit. Subjects who cannot safely enter the scanner will not be eligible to participate in the scanning portion of the study but may elect to remain in the study as a non-imaging subject.

## **Inclusion/Exclusion Criteria #2**

Name the subject group/sub sample

Participants without Neuroimaging (not currently recruiting)

Create or insert table to describe the inclusion criteria and methods to ascertain them

Participants with NSSI without Neuroimaging: Inclusion Criteria	Method of Ascertainment
1. Age 18-60	Interview
2. Frequent current NSSI (including cutting in which the skin is broken; self-hitting in which there is bruising; or burning in which there is evidence of a burn. Will not enroll if skin-picking or scratching is the only form of self-injury): has engaged in $\geq 2$ episodes of NSSI in the two months prior to enrollment	Self Injurious Thoughts and Behaviors (SITBI) scale and clinical interview
3. Capacity to provide informed consent	Clinical interview
4. If carries a diagnosis of bipolar I or II disorder, taking a therapeutic dose of a mood stabilizer	SCID, clinical interview, therapeutic blood levels if applicable

Create or insert table to describe the exclusion criteria and methods to ascertain them

Participants without Neuroimaging: Exclusion Criteria	Method of Ascertainment
1. Unstable medical conditions based on medical history of physical examination	Medical history (by a physician), physical exam, screening lab tests as performed through co-enrollment in IRB #4815
2. Current psychotic disorder, mania, hypomania, intellectual disability	Psychiatric interview, SCID
3. Dermatologic condition resulting in non-intact skin on the scalp	Medical history, physical exam
4. Significant suicidal ideation with a plan and intent that cannot be managed safely as an outpatient	C-SSRS, clinical interview
5. Pregnancy, currently lactating, or planning to conceive during the course of study participation	serum HCG at time of screening
6. A neurological disease or prior head trauma with evidence of cognitive impairment. Subjects who endorse a history of prior head trauma and score $\geq 1.5$ standard deviations below the mean	Clinical interview and medical history, Trailmaking A&B as needed

on the Trailmaking A&B will be excluded from study participation

7. Current alcohol or substance use disorder that is moderate or severe according to DSM-5 criteria SCID, urine drug test, clinical interview

8. Current opiate use disorder SCID, urine drug test, clinical interview

9. Current medical or recreational use of any opiate medication Clinical interview, urine drug test

Individuals who initiated or increased the dose of concurrent psychiatric medications (including

10. antidepressants, anxiolytics, antipsychotic medications, mood stabilizers, and benzodiazepines) within two weeks prior to enrollment Medical history, clinical interview

11. Individuals who initiated psychotherapy within two weeks prior to enrollment Clinical interview

